7.3 Withdrawal criteria (endpoints)

Treatment with the study drug will be terminated **immediately** during the study for any of the following reasons:

- Patient with virologic failure
- Pregnancy during the study.
- Express wish of the patient
- Medical criteria
- Exitus

Treatment with the study drug **may** be terminated during the study for any of the following reasons:

- The medical investigator determines that a SAE is possibly or likely related to the study drug.
- Failure to administer, evaluate, or other study requirements.

8. Treatment of Subjects

8.1 Treatment Branches

Randomization to two treatment groups: A or B

GROUP A (control): ATRIPLA® at standard daily dose (1 tablet daily) for a period of 24 weeks

GROUP B (experimental): ATRIPLA® at a dose three days per week (1 tablet Monday, Wednesday and Friday) for a period of 24 weeks

8.2 Concomitant and rescue medication

Any concomitant medication must be reflected in the CRF in an appropriate way (detailing the product, dosage, route, days of administration, reason for treatment, etc.).

Treatments not allowed:

The administration of treatments that are contraindicated with the study drugs will not be allowed. (see annex technical sheets)

8.3 Compliance monitoring

Adherence: to ensure the control and registration of medication, an adherence questionnaire will be added to the data collection notebook. At each visit, the investigator will ask the patient about treatment adherence.

Tablet count: The patient will be asked to bring any leftover medication or empty bottles with them to check whether or not they have taken all the capsules or tablets of the medication since the previous visit.

9. Effectiveness Assessment

9.1 Efficiency parameters

Virological tests

a. Determination of viral load

Standard determination of viral load (detection limit 37 copies/mL) Virologic failure will be defined as:

In case of detection of plasma viral load (≥ 37 copies/mL), the determination of plasma viral load should be repeated during the following week for confirmation. If the result of the confirmatory determination is ≥ 37 copies/mL

b. Methods of Analysis and Sensitivity

The standard HIV-1 viral load in the plasma sample will be previously performed using the commercial VERSANT HIV-1 RNA 1.0 Assay (kPCR) (SIEMENS HEALTHCARE DIAGNOSTICS) technique with a sensitivity of up to 37 copies/mL. The manufacturer's recommendations will be followed.

Ultrasensitive viral load (detection limit 1 copy/mL)

By ultracentrifugation (170000g, 30 minutes, 4°C) the HIV-1 virions present in 7mL of plasma will be concentrated, a volume to which will have been added a known concentration of an RNA transcript used as a non-competitive internal control for the monitoring of ultracentrifugation, extraction and amplification processes. The supernatant will be removed leaving a residual volume of 200 L, from which the viral RNA will be extracted using the commercial QIAamp MinElute Virus Spin (QIAGEN) kit, following the manufacturer's recommendations. The RNA obtained will be aliquoted and frozen at -80°C until use. The ultrasensitive quantification of the HIV-1 viral load will be performed by means of a one-step RT-PCR duplex in real time, using the STRATAGENE Mx3005P platform. For the amplification and detection of a conserved region of the HIV-1 gag gene, the primers and probes previously described by Palmer et al (2003) will be used. To detect the non-competitive internal control added to the sample, a set of specific primers and probe described above will be used (Almansa et al [PMID 21880131], Anton et al [PMID 20955912]). To carry out the quantification of the HIV-1 viral load and the internal control, two standard lines of serial dilutions from a known concentration of a standard will be amplified in parallel, one for the determination of the HIV-1 viral load and the other for internal control. Each quantification test will be performed in triplicate for each of the samples and for each of the dilutions of the standard line. In each of the tests, negative plasma samples will be used as a target to minimize the impact of possible contaminations in some of the steps of the process. For the quantification (copies/mL) of HIV-1 viral load, only those results within the linear range of the assay ($R>0.95$) will be considered. Initially, the result of the HIV-1 viral load will be validated in those samples where the recovery of internal control is greater than 55%, as described by Palmer et al (20), although this must be previously demonstrated in the process of optimizing our methodology.

The specific PCR product obtained with the primers specific for a conserved region of the gag gene previously described by Palmer et al (20) will be cloned into a pGEM-T Easy Vector (PROMEGA) plasmid that will be linearized by the restriction enzyme Spel (NEW ENGLAND BIOLABS). This plasmid, which contains a T7 promoter for RNA polymerase, will be transcribed in vitro using the commercial MEGAscript Kit (AMBION). Purification of the RNA transcript obtained as a standard control for HIV-1 quantification will be performed using the commercial MEGAclear Kit (AMBION). The concentration and integrity of the RNA transcript obtained will be determined using the BioAnalyzer (AGILENT) platform. From a known concentration of this standard standard, a bank of dilutions will be generated to determine the efficiency, linearity range and lower limit of sensitivity.

The RNA transcript used as an internal control, based on a conserved region of the coding sequence of the M1 protein of the influenza A virus, has previously been used in the quantification of the influenza A (H1N1) pdm09 virus in our laboratory (Almansa et al [PMID 21880131], Anton et al [PMID 20955912]). For its synthesis, the methodology described in the previous section was followed. The percentage of internal control, added to the plasma sample prior to ultracentrifugation, which is recovered and from which we will consider the results of the HIV-1 viral load valid, will be validated in our laboratory, initially considering as good the 55% recovery previously described by Palmer et al (20).

B) HIV-1 viral reservoir study:

The study of the viral reservoir will be determined based on the methodology initially described by the group of Nicholas Chomont (19) modified by the Laboratory of [name]. It will be made from 50×10^6 frozen peripheral blood mononuclear cells. A purification of CD4+ T-cells by negative depletion will be performed. These purified cells will be activated in the presence of anti-CD3/CD28. The culture should be maintained for 9 days in the presence of a cocktail of antiretrovirals (zidovudine, efavirenz, and raltegravir) to prevent further rounds of infection and a reactivation of viral production. Finally, viral production will be quantified at 3, 6 and 9 days, from the supernatant of the cultures, by ultrasensitive RT-qPCR and p24 antigen assessment by capture ELISA.

C) Immunological studies:

The study of activation markers in the different CD4 and CD8 lymphocyte subpopulations will be carried out by extracellular staining with conjugated antibodies for subsequent analysis by flow cytometry.

The detection of cleaved circular DNA (TRECs) after genetic rearrangement of the T cell receptor (TCR) will be carried out by the usual methods (real-time PCR).

Determination of apoptosis will be performed using the annexin V staining method.

D) Pharmacokinetics

All patients will be proposed to be included in the pharmacokinetic substudy. At baseline, each of them should have their plasma levels determined in efavirenz in the morning before the next daily dose.

This determination will be repeated at week 24 of treatment. For patients who continue with the daily treatment, the extraction will be carried out any day in the morning; and for those randomized to receive ATRIPLA® on Monday, Wednesday and Friday, the extraction will be carried out on a Monday morning because it is the day of the week when the plasma concentration of efavirenz must be lower due to the maximum dose interval.

E) Safety

To evaluate sleep quality, the "Pittsburgh Sleep Quality Index" will be carried out, available in its validated Spanish version (<http://www.medigraphic.com/pdfs/gaceta/gm-2008/gm086e.pdf>).

The plasma concentration of vitamin 25OHD3 will be determined by immunoassay.

The estimated glomerular filtration rate will be calculated using the usual formula, available in http://www.nephron.com/MDRD_GFR.cgi.

10. Safety Rating

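### The internal control for the single-copy viral load assay is an RNA transcript that would barely sediment, so its recovery cannot show whether virions were lost in the spin

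*Combined protocol and SAP*

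**What the plan says.** Section 9.1 (ultrasensitive viral load, detection limit 1 copy/mL) describes the concentration step: "By ultracentrifugation (170000g, 30 minutes, 4°C) the HIV-1 virions present in 7mL of plasma will be concentrated". The control goes into that same plasma before the spin. It is "an RNA transcript used as a non-competitive internal control for the monitoring of ultracentrifugation, extraction and amplification processes", so ultracentrifugation is one of the three steps it is given to monitor. Afterwards, "The supernatant will be removed leaving a residual volume of 200 L"; the unit prefix was evidently lost in text conversion, and I read it as 200 microlitres.

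The control is a transcript of a conserved part of the influenza A M1 coding sequence. On how it was made, the section says: "For its synthesis, the methodology described in the previous section was followed". That method, set out for the HIV-1 standard, is in vitro transcription from a linearised plasmid followed by purification. No capsid, envelope or other packaging is described.

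The validity rule is that "the result of the HIV-1 viral load will be validated in those samples where the recovery of internal control is greater than 55" per cent. The denominator is the amount put in before the spin: "The percentage of internal control, added to the plasma sample prior to ultracentrifugation, which is recovered". Section 9.1 twice marks 55% as a starting value, taken from a cited assay publication and to be confirmed in the sponsor's own laboratory.

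The proportion below 1 copy/mL at week 24 is the first secondary endpoint in section 6.1. Section 6.6 stores the samples at -80°C and defers these assays to the end of the study. Section 11.5 rules out imputation.

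**The concern.** A control for a pelleting step must pellet as its target does. HIV-1 virions are particles and go to the bottom of the tube. A purified transcript of a gene fragment is a small dissolved molecule, and most of it would be discarded with the supernatant. Its recovery then reflects the volume kept, plus extraction and amplification, and says next to nothing about how many virions were kept.

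The justification (section 4) relies on this assay to reveal any effect of the reduced dose on replication that the 37 copies/mL assay would miss. A result below 1 copy/mL is reassuring only if virions present in the plasma reached the PCR. If they were lost unnoticed, the error runs towards reassurance.

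**Working it through.** **Figure in the plan.** The 55% limit comes without a derivation, so there is nothing to reproduce. The question is whether the described control could reach it, and whether its recovery would respond to virion loss.

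**Inputs from section 9.1.** Plasma 7 mL; retained volume 0.2 mL; 170,000 g for 30 min (1,800 s); limit 55%.

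**Step 1, document figures only.** A control that stays dissolved is kept in proportion to volume: 0.2/7 = 2.9%. That is 0.55/0.0286 = 19 times below the limit. Keeping 55% of such a control would mean retaining 0.55 × 7 = 3.85 mL.

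**Step 2, allowing some sedimentation.** These inputs are assumptions, not in the documents: transcript 4–23 S, virion 500–700 S, liquid column h = 40–80 mm, viscosity 1 to 4 times water, uniform starting distribution, constant field.

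- Distance moved: d = S × 10⁻¹³ × (170,000 × 9.81) × 1,800 / relative viscosity, which is 0.30 mm per S at viscosity 1.
- Pelleted share: f = min(1, d/h).
- Recovery: f + (1 − f) × 0.0286.
- Upper corner for the transcript (23 S, viscosity 1, 40 mm): d = 6.9 mm, f = 0.173, recovery = 0.173 + 0.827 × 0.0286 = 19.6%.
- Lower corner (4 S, viscosity 4, 80 mm): d = 0.30 mm, f = 0.004, recovery = 3.2%.
- Pelleted share needed for 55%: (0.55 − 0.0286)/(1 − 0.0286) = 53.7%.

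| Relative viscosity | Transcript recovery | Virion recovery | S needed for 55% |
|---|---|---|---|
| 1 | 4–20% | 100% | 72–143 |
| 3 | 3–8% | 64–100% | 215–429 |
| 4 | 3–7% | 48–100% | 286–572 |

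A narrower set of assumptions (transcript 4–13 S, virion 600 S, column 30–70 mm, viscosity 1–3) gives 3–16% for the transcript, 86–100% for virions, and about 54–376 S to reach 55%. In both sets the required value lies well above the transcript's assumed range.

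**Step 3, response to virion loss.** The recovery formula for the transcript contains no term for virions. With no sedimentation it is 2.9% whether virion loss is 0%, 50% or 90%. If the spin failed altogether (f = 0), virion recovery would drop to 2.9%, whereas transcript recovery at viscosity 3–4 would move only from 3–8% to 2.9%.

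**Step 4, the limit kept at 55%.** As an illustration, assume recovery varies lognormally between samples with log-SD 0.5. The pass probability is 1 − Φ(ln(0.55/m)/0.5), where m is the median recovery. For m = 10% it is 0.03%. For m = 20%, the top of the range, it is 1 − Φ(2.02) = 2.2%. With 60 patients and two time points there are up to 120 samples, so about 120 × 0.0215 = 2.6 would pass at best.

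**Step 5, the limit lowered.** The rule then no longer screens for virion loss. If results are not corrected for virion recovery (no such correction is described), a sample with recovery r reads below 1 whenever its true level is below 1/r. At r = 86%, the low end of the narrower set, this is 1/0.862 = 1.16 copies/mL. At r = 48%, the low end of the wider set, it is 1/0.484 = 2.07 copies/mL.

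**The case against.** The strongest reply is that 55% is provisional. Section 9.1 requires it to be demonstrated locally, and section 6.6 defers the assays on frozen samples. A control recovering a few per cent would be noticed during optimisation, before any trial sample was used. This stands. A reader might infer that the trial will lose nearly all its single-copy results. The documents do not support that, because it would require the laboratory to skip its own validation or ignore the outcome. The reply does not cure the defect, though: validating another percentage does not make the transcript behave like a virion.

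Three further objections have weight.

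- That the control is unpackaged is inferred from the synthesis method and the absence of any packaging step. The cited laboratory publications were not available and might say more.
- Sedimentation coefficients, tube geometry and viscosity are assumed. A flat claim that the transcript cannot sediment goes too far; it sediments negligibly across the assumed ranges. At the unfavourable end (48%) even a particle control could miss 55%, so the cut-off needs validating for any control.
- Both arms use the same assay, so virion loss should be largely non-differential. It would dilute a difference between arms and raise the proportion below 1 copy/mL in both. It would not by itself favour one arm.

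**Conclusion.** The point holds in a limited form. As described, the control cannot monitor the ultracentrifugation step assigned to it. Its expected recovery is 2.9% from the plan's own volumes if it does not sediment, and about 3–20% under the assumed ranges, against a provisional limit of 55%. Keeping the limit would fail almost all samples. Lowering it would leave virion recovery unchecked, so a false result below 1 copy/mL could pass.

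This rests on the transcript being unpackaged, on the retained volume being 200 microlitres, and on the stated sedimentation assumptions. RNase degradation in plasma would lower recovery further, but the documents give no figure and the conclusion does not need it.

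A reader might also infer that large virion losses, say 80%, are to be expected. They are not shown: the model gives virion recovery of 86–100% under the narrower assumptions and 48–100% at worst, and no other loss is quantified. The finding is that a loss would go undetected, not that one will occur. The primary endpoint uses the commercial 37 copies/mL assay and is unaffected.

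**What to change.** Amend section 9.1 before any stored trial sample is assayed.

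- Preferred: replace the transcript with an intact-particle control carrying the same M1 target, for example a quantified stock of inactivated influenza A virus, added to the 7 mL before the spin. The existing primers, probe and control standard line can stay. Validate the recovery cut-off on that control during the optimisation already planned, and fix it before trial samples are run.
- If the transcript is kept: add it at lysis to the 200 microlitre concentrate, and state that it monitors extraction and amplification only. Virion recovery in the spin would then have no per-sample check, and the report should say so.

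The cost is preparing and titrating one virus stock and a spiking check within the planned optimisation, plus the change of wording. I judge this small, although the documents give no costing. It needs no extra visits, blood or patients.

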10.1 Detection and recording of Adverse Events

It is the investigator's responsibility to detect and document any event that meets the criteria and definitions of adverse event (AE) or serious adverse event (SAE) as set forth in this protocol. During the study, the existence of adverse events, whether serious or not, will be checked in accordance with the definition given in this section of the protocol.

a) Minimum information to be specified:

Description/definition:

Adverse event (AE) is any adverse health event in a patient or clinical trial subject treated with a medicine, even if it is not necessarily causally related to that treatment. Therefore, it can be any unfavorable and unintended signs (including an abnormal laboratory finding), symptom, or illness temporarily associated with the use of an investigational drug, whether or not related to the investigational drug.

Laboratory abnormalities of clinical importance that meet one or more of the following criteria are also considered AEs:

- It requires additional intervention or treatment.
- Requires a modification of the dose.

- It is accompanied by a clinical manifestation.

Any analytical anomaly that the investigating physician considers to be of clinical importance must be recorded as such in the printed copy of the laboratory report, indicating the physician's initials and the date of revision. An AA is also considered to be any event associated or observed in conjunction with an accidental or intentional overdose of the product, or with abuse or withdrawal of the product.

All AEs will be recorded in the subject's medical record and in the eCRDe. The start and end dates of each AA, the intensity and the relationship with the study drug will be recorded.

The criteria for subject treatment, dose discontinuation, dosage adjustment, withdrawal, or treatment changes will only apply to toxicities attributable to the study drugs (i.e., efavirenz, tenofovir, and emtricitabine).

The classification system for drug toxicity is set out in the DAIDS Table for Grading the Intensity of Adverse Events in Adults and Children, which can be found on the DAIDS RSC website: <http://rsc.tech-res.com/safetyandpharmacovigilance/>.

In addition, for each AA, the measures taken or the outcome (e.g. hospitalization, discontinuation of treatment) will be recorded.

Adverse reaction (AR) is any harmful, unintended reaction to an investigational drug, regardless of the dose administered. In this case, there is a suspicion of a causal relationship between the investigational drug and the adverse event.

Serious adverse event (SAE) is any adverse event that, at any dose, results in death, threatens the life of the subject, makes hospitalization necessary or prolonged hospitalization, results in permanent or significant disability or disability, or results in a congenital anomaly or malformation. For the purposes of notification, suspected adverse events that are considered medically significant, even if they do not meet the above criteria, will also be treated as serious, including major medical events that require intervention to prevent one of the consequences described above from occurring. Likewise, all suspected transmission of an infectious agent through a drug will be reported as serious. Examples of these events include allergic bronchospasm requiring intensive treatment in an emergency department or at the individual's home, blood dyscrasia or seizures that do not require hospitalization, or the development of drug dependence or abuse.

Medical and scientific judgement should be used to decide whether other situations that have not resulted in the outcomes listed in the above definitions should be reported as SAGs.

A life-threatening term is defined as a situation where, in the opinion of the physician, the patient at the time of the adverse event or adverse reaction is at real risk of death.

Hospitalization or prolongation of a hospitalization is a criterion for considering an AA to be serious. Only admission in which the patient spends the night in the hospital should be considered as hospitalization. The following situations will not meet the AAG criteria:

- if hospitalization or prolongation of hospitalization is necessary to perform a procedure required by the protocol (for example, if day or night visits will be made for biopsies or surgeries required by the protocol).
- if hospitalization or prolongation of hospitalization is part of the facility's routine procedure (e.g., removal of a stent after surgery)

- in case of scheduled hospitalization for a pre-existing process that has not worsened (e.g. scheduled hospitalization for the implantation of a knee prosthesis for a previous osteoarthritis process)

Grade IV laboratory alterations will be considered AAG.

DO NOT confuse the concept of "serious" with "severe" which refers to the intensity of the adverse event or adverse reaction.

Unexpected serious adverse reaction (RAGI) is a serious adverse reaction whose nature or severity does not correspond to the information regarding the product (for example, the investigator's manual in the case of an investigational medicinal product not authorised for marketing or the product label in the case of an authorised medicinal product).

b) Imputability criteria.

The causal relationship between the investigational product and the occurrence of AA/AAG shall be established on the basis of clinical judgment. To this end, other causes will be considered and studied, such as the natural history of the underlying diseases, concomitant treatment, other risk factors and the temporal relationship of the event with the investigational product. In addition, the technical data sheet of the products will be consulted.

In order to analyse the possible cause-effect relationship, the temporal relationship between the administration of the drug and the AA, possible alternative causes, the evolution (complete remission, partial recovery, death, sequelae, persistence), persistence or not after the suspension of administration, reappearance with the readministration of the product or the prior knowledge of said event coinciding with the known or expected response pattern of the drug under study will be considered.

The causal relationship of an AA with the medication under study will be established according to the following definitions:

Unlikely relationship: The adverse event does not occur after a plausible chronological sequence related to the administration of the product under study and/or is reasonably explainable by other factors, such as the patient's clinical status or other concomitant therapeutic, toxic, or environmental interventions. In addition, it does not match the known or expected response pattern of the drug.

Possible relationship: the adverse event occurs after a plausible chronological sequence related to the administration of the product under study, but can also be explained by the patient's clinical status or other concomitant therapeutic, toxic, or environmental interventions. It also matches the known or expected response pattern of the drug.

Probable relationship: The adverse event occurs after a plausible chronological sequence related to the administration of the product under study, cannot be reasonably explained by the patient's clinical status or other concomitant therapeutic, toxic, or environmental interventions, and after withdrawal or reduction of the dose of the suspect drug the event follows a logical clinical sequence. It also matches the known or expected response pattern of the drug.

Very likely relationship: the adverse event occurs after a plausible chronological sequence related to the administration of the product under study, cannot be reasonably explained by the clinical status of the patient or other concomitant therapeutic, toxic or environmental interventions, after withdrawal or reduction of the dose of the suspect drug the event follows a logical clinical sequence and it is necessary that after the readministration of the suspicious drug the adverse event reappears. It also matches the known or expected response pattern of the drug.

Unrelated: Adverse event clearly due to causes unrelated to the medication under study and the criteria for another causal relationship are not met.

Non-assessable relationship: any notification that suggests an adverse effect, which cannot be judged because the information is insufficient or contradictory and which cannot be supplemented or verified.

